12.2.8 Reporting Safety Information to the IRB

The Investigator must promptly report to the Investigator's IRB all unanticipated problems involving risks to patients. This includes death from any cause and all SAEs occurring during the study, regardless of the assessed causality.²³

12.2.9 Record Retention

All drug accountability records, eCRFs, source data and related regulatory documents must be retained for at least two years following completion of the study or Test product approval for marketing by the FDA.

12.2.10 Study Monitoring and Auditing

[REDACTED] will be responsible for monitoring the study according to Good Clinical Practice and applicable regulations. Monitoring visits are for the purpose of confirming adherence to the protocol and to verify complete and accurate data collection. The clinical site will make all

CONFIDENTIAL PROTOCOL

A Randomized, Double-Blind, Placebo-Controlled, Parallel-Design, Multiple-Site Study to Evaluate the Therapeutic Equivalence of Estradiol Vaginal Cream, USP, 0.01% (Prasco LLC) to Estrace[®] Cream (Estradiol Vaginal Cream, USP, 0.01%) (Warner Chilcott) in the Treatment of Vulvar and Vaginal Atrophy, 71759501

records associated with the study available to [REDACTED] representative during such visits and audits.

The study may be subject to audit by the Sponsor, Sponsor Representative or by regulatory authorities. If such an audit occurs the Investigator must agree to allow access to required patient records. By signing this protocol, the Investigator grants permission to personnel from the Sponsor, its representatives and appropriate regulatory authorities for on-site monitoring of all appropriate study documentation, as well as on-site review of study procedures.

12.2.11 End of the Trial

The end of the trial is defined as the time at which the last patient has completed their last visit in the study. Upon completion of the study, the study product will no longer be available to the patient but the Investigator can, at their discretion, discuss alternative treatments with the patient.

12.2.12 Clinical Study Report

At the end of the study a full report per requirements of Sponsor and regulatory authorities will be prepared which will include a narrative of the clinical conduct and results of the study, a statistical report including a description of the analysis performed, and other documentation as may be appropriate. The report will be in electronic format according to eCTD and International Conference on Harmonisation formatting standards and guidelines.²⁴

CONFIDENTIAL PROTOCOL

A Randomized, Double-Blind, Placebo-Controlled, Parallel-Design, Multiple-Site Study to Evaluate the Therapeutic Equivalence of Estradiol Vaginal Cream, USP, 0.01% (Prasco LLC) to Estrace® Cream (Estradiol Vaginal Cream, USP, 0.01%) (Warner Chilcott) in the Treatment of Vulvar and Vaginal Atrophy, 71759501

14.0 APPENDICES

14.1 APPENDIX A: Clinical Laboratory Testing

CLINICAL LABORATORY TESTING

As part of the Screening Procedures the blood and cytology samples will be obtained for the following laboratory evaluations:

Serum FSH

Fasting Triglycerides

Vaginal Cytology

PAP Smear (as appropriate)

All samples will be sent to the central laboratory:

CONFIDENTIAL PROTOCOL

A Randomized, Double-Blind, Placebo-Controlled, Parallel-Design, Multiple-Site Study to Evaluate the Therapeutic Equivalence of Estradiol Vaginal Cream, USP, 0.01% (Prasco LLC) to Estrace[®] Cream (Estradiol Vaginal Cream, USP, 0.01%) (Warner Chilcott) in the Treatment of Vulvar and Vaginal Atrophy, 71759501

14.2 APPENDIX B: Definitions and Severity ratings for Signs and Symptoms

Vaginal Dryness		
Score	Severity	Description
0	None	No noticeable lack of vaginal lubrication or secretions reported or observed
1	Mild	Episodic loss of lubrication/secretions or noticed some reduction in general secretions, does not interfere with daily activities
2	Moderate	Symptom present most of the time, and noticeable but overall is tolerable and does not interfere with daily activities
3	Severe	Very minimal or no natural vaginal lubrication/secretions almost all of the time and interferes with normal activities

Vaginal/Vulvar Irritation/Itching		
Score	Severity	Description
0	None	No irritation or itching reported.
1	Mild	Occasional irritation/itching but does not interfere with daily activities
2	Moderate	Frequent irritation/itching that can be uncomfortable but generally does not interfere with daily activities
3	Severe	Very frequent or continuous irritation/itching of the vaginal area, may interfere with daily activities.

Dysuria		
Pain or discomfort during urination		
Score	Severity	Description
0	None	No pain or discomfort during urination reported.
1	Mild	Occasional or slight discomfort during urination but tolerable
2	Moderate	Some discomfort during urination at least 50% of the time which can be painful but overall tolerable.
3	Severe	Urination nearly always painful, usually intolerable and causing disruption to daily activities

CONFIDENTIAL PROTOCOL

A Randomized, Double-Blind, Placebo-Controlled, Parallel-Design, Multiple-Site Study to Evaluate the Therapeutic Equivalence of Estradiol Vaginal Cream, USP, 0.01% (Prasco LLC) to Estrace[®] Cream (Estradiol Vaginal Cream, USP, 0.01%) (Warner Chilcott) in the Treatment of Vulvar and Vaginal Atrophy, 71759501

Vaginal Pain during Sexual Activity		
Suffers discomfort or pain during sexual activity that may be restrictive.		
Score	Severity	Description
0	None	No discomfort or pain
1	Mild	Some feeling of vaginal soreness or pain, during or after sexual activity. Does restrict frequency of or type of sexual activity.
2	Moderate	Vaginal pain during sexual activity such that frequency and type of sexual activity have been disrupted. Lubrication may be needed for penetration
3	Severe	Vaginal penetration very painful and impossible without vaginal lubrication. Discomfort such that frequency of sexual activity significantly reduced.

Vaginal bleeding during or after sexual activity		
At each visit each patient must also clearly identify which is the most bothersome sign/symptom to her, even if she rates two or more symptoms the same severity rating.		
Score	Severity	Description
0	Absent	No vaginal bleeding observed
1	Present	Bleeding observed during or soon after vaginal activity

CONFIDENTIAL PROTOCOL

A Randomized, Double-Blind, Placebo-Controlled, Parallel-Design, Multiple-Site Study to Evaluate the Therapeutic Equivalence of Estradiol Vaginal Cream, USP, 0.01% (Prasco LLC) to Estrace[®] Cream (Estradiol Vaginal Cream, USP, 0.01%) (Warner Chilcott) in the Treatment of Vulvar and Vaginal Atrophy, 71759501

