10.6.6 Signs and Symptoms

At each visit, the blinded clinical staff or Investigator will question the patient regarding the severity of their symptoms. See Appendix B for rating scales. The following symptoms will be evaluated:

- Vaginal Dryness
- Vaginal/Vulvar irritation/itching
- Dysuria
- Vaginal Pain associated with Sexual Activity
- Vaginal Bleeding

The severity of each symptom will be recorded on the source documents. The patients will be asked to identify which symptom is considered to be the most bothersome symptom at each visit.

CONFIDENTIAL PROTOCOL

A Randomized, Double-Blind, Placebo-Controlled, Parallel-Design, Multiple-Site Study to Evaluate the Therapeutic Equivalence of Estradiol Vaginal Cream, USP, 0.01% (Prasco LLC) to Estrace[®] Cream (Estradiol Vaginal Cream, USP, 0.01%) (Warner Chilcott) in the Treatment of Vulvar and Vaginal Atrophy, 71759501

At Visits 1 and 2, the most bothersome symptom must have a score of moderate or severe (for vaginal dryness, vaginal/vulvar irritation/itching, dysuria, or vaginal pain associated with sexual activity) or present (for vaginal bleeding) to be eligible for inclusion in the study.

The worsening in severity of the Signs and Symptoms need not be additionally included as AEs unless the patient requires additional treatment or in the opinion of the Investigator

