11.5 Efficacy Endpoints

Primary Efficacy Endpoint

The primary efficacy endpoint is the proportion of patients in each treatment group that are identified as Responders at the end of the treatment period evaluated on Day 8 or Day 9.

A “Responder” is defined as a patient with at least a 25% reduction from baseline in the sum of % basal/parabasal + % intermediate cells on vaginal cytology AND vaginal pH < 5.0 with a change from baseline vaginal pH of at least 0.5.

Secondary Efficacy Endpoint

The secondary efficacy endpoint is the proportion of patients in each treatment group that are considered a Treatment Success at the end of the treatment period evaluated on Day 8 or Day 9.

CONFIDENTIAL PROTOCOL

A Randomized, Double-Blind, Placebo-Controlled, Parallel-Design, Multiple-Site Study to Evaluate the Therapeutic Equivalence of Estradiol Vaginal Cream, USP, 0.01% (Prasco LLC) to Estrace[®] Cream (Estradiol Vaginal Cream, USP, 0.01%) (Warner Chilcott) in the Treatment of Vulvar and Vaginal Atrophy, 71759501

A “Treatment Success” is defined as a score of 0 or 1 on Day 8 or Day 9 for the symptom identified at baseline as the most bothersome. This evaluation will be based on (one) patient self-assessed symptom of VVA (vaginal dryness, vaginal and/or vulvar irritation/itching, dysuria, or vaginal pain associated with sexual activity) on a scale of 0 to 3 where 0 = none and 3 = severe. Evaluation of vaginal bleeding during sexual activity will be based on a Score of 1 (presence) if it is identified by the patient as the most bothersome symptom at baseline and a score of 0 (absent) on Day 8 or Day 9. Refer to Appendix B for rating scales.

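### The Mild anchor for vaginal pain says sexual activity is restricted, so it overlaps with Moderate at the line that sets symptom entry and the secondary Treatment Success endpoint

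*Protocol*

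**What the plan says.** Protocol 14.2 (Appendix B) rates vaginal pain during sexual activity from 0 to 3.

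- Score 0 is no discomfort or pain.
- Score 1 (Mild) is some soreness or pain during or after activity, followed by "Does restrict frequency of or type of sexual activity".
- Score 2 (Moderate) is "Vaginal pain during sexual activity such that frequency and type of sexual activity have been disrupted", with lubrication possibly needed.
- Score 3 (Severe) is very painful penetration, impossible without lubrication, and "Discomfort such that frequency of sexual activity significantly reduced".

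SAP Appendix A prints the same Mild anchor. Nothing elsewhere in either document corrects it.

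The scale is used in two places. Under Protocol 10.6.6, at Visits 1 and 2 "the most bothersome symptom must have a score of moderate or severe" for the woman to be eligible (bleeding is rated as present or absent instead). Under Protocol 11.5 and SAP section 7, Treatment Success is "a score of 0 or 1 on Day 8 or Day 9 for the symptom identified at baseline as the most bothersome". Vaginal pain is one of the symptoms graded this way.

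Treatment Success is the secondary endpoint. Protocol 11.6 and SAP 8.2.1 rest both the equivalence and the superiority declarations on the primary endpoint alone. SAP 8.2.2 calls the secondary equivalence test supportive.

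**The concern.** Mild and Moderate should be distinguishable, because the plan splits the scale between them. As printed, both describe pain that limits sexual activity. The same state can therefore be graded 1, which means refused at entry or a success at the end. It can equally be graded 2, which means eligible at entry or a failure at the end.

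Vaginal pain is the only symptom in the appendix whose Mild grade asserts a functional limit. The Mild anchor for irritation/itching, for comparison, is "Occasional irritation/itching but does not interfere with daily activities".

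At stake are the secondary endpoint and the symptom entry criterion, for women who name this symptom as most bothersome. Raters are blinded, so misgrading should occur at similar rates in all arms. That pulls differences toward zero: Test and Reference look slightly more alike on the supportive equivalence analysis, and secondary superiority over Placebo becomes slightly harder to show.

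**Working it through.** The plan gives no figure on this point to reproduce. The check compares the anchors and then works one illustration.

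**Three patient states against the printed anchors**

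1. *Pain limits both frequency and type of activity.* Mild applies, because its *or* is inclusive. Moderate applies too. The score is 1 or 2, on opposite sides of both cuts.
2. *Slight soreness, no restriction.* Score 0 is excluded because there is some pain. Score 1 is not met because it asserts restriction. No level matches. This gap has little consequence at the cut, since 0 and 1 are treated alike at entry and at the end, but it shows that the anchor is faulty.
3. *Enters as Severe and improves to state 1.* On Day 8 or Day 9 she can fairly be scored 1 (success) or 2 (failure).

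**Does another feature separate Mild from Moderate?** For dryness and irritation/itching, how often the symptom occurs separates the two grades. Pain has no such axis. Its remaining markers are *or* against *and*, restriction against disruption, and possible need for lubrication. The move from *or* to *and* does not continue upward, since Severe returns to frequency alone. The lubrication marker is permissive, and Protocol 10.3.3 asks patients to refrain from vaginal lubricants.

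**Illustrative size (all inputs assumed; none is in the documents)**

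- s, share of women whose most bothersome symptom is vaginal pain: 0.30 to 0.50.
- f, fraction of true failures in that group scored as successes, the same in every arm: 0.20.
- d, true difference in success rate, the same in all women: 20 points.

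Within the pain group, the observed rate in an arm with true rate p is p + f(1 - p). The observed difference is therefore (1 - f)d = 0.8 x 20 = 16 points.

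Over all women, the observed difference is s(1 - f)d + (1 - s)d = d(1 - fs):

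- s = 0.30: 20 x (1 - 0.06) = 18.8 points.
- s = 0.50: 20 x (1 - 0.10) = 18.0 points.

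The loss on the analysed difference is 1.2 to 2.0 points.

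**The case against.** **The levels are not identical.** Mild and Moderate differ in *or* against *and*, in restriction against disruption, and in the mention of lubrication. They also carry different labels and scores. This stands: some gradation remains, and a reading of complete overlap would go too far. It does not give a rater a dividing line for a woman limited in both respects.

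**A lost negative is not shown.** A reader might infer from the other Mild anchors that a *not* was dropped. However, the Moderate anchors for dryness and irritation/itching also deny interference (the latter in general terms), Mild dysuria does not mention it, and the pain scale's own header allows that pain may be restrictive. The case report form booklet listed in the SAP introduction is not available here. The cause is plausible, not established.

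**Misgrading needs inconsistent scoring.** For a woman whose state does not change, it does: she must be scored 2 or 3 at Visits 1 and 2 and then 1 at Visit 3. That limits how often this route can operate. A woman who improves from Severe to a partly restricted state needs no inconsistency.

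**The effect could be read as large.** A reader might multiply a 30-50% share by 10-20% rescored and infer a 3-10 point shift in the overall success rate (0.3 x 0.1 to 0.5 x 0.2). Those inputs are also assumed, and a shift common to all arms cancels in the difference, which is what the plan tests.

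**No declaration depends on it.** This stands in full.

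**Conclusion.** The defect holds on the text of both documents: the Mild anchor overlaps with Moderate and leaves mild soreness without restriction unscored. The overlap lies at the line used for symptom entry and for Treatment Success, so it is an operative rating rule and worth correcting.

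Its reach is limited to women whose most bothersome symptom is vaginal pain, and to the entry criterion and the supportive secondary endpoint. A reader might infer that the equivalence conclusion is at risk. The documents do not support that, because both declarations rest on cytology and pH, which these ratings do not measure.

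The size cannot be computed from the documents. The fall from 20 to about 18.0-18.8 points rests on the assumed share, the assumed 20% misgrading in one direction, equal misgrading across arms and an equal true difference in all women. It shows a modest pull toward zero and is not an estimate.

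**What to change.** 1. Check the Mild anchor against the rating form used at the sites and against the source scale.
2. Reconcile Protocol Appendix B, SAP Appendix A and the form so that Mild and Moderate do not overlap on restriction. Take the wording from that check, without presuming that a negative was lost.
3. State in the SAP which wording raters used.
4. If ratings were already collected on the printed text, prespecify one supportive analysis of the secondary endpoint that excludes women whose baseline (Visit 2) most bothersome symptom is vaginal pain. Under SAP section 4 the statistician receives the randomization schedule only after database lock, so this can be fixed while blinded.

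Counting only a score of 0 as success for these women is not a substitute. It puts a different, stricter endpoint in place for one subgroup and does not repair the grading.

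The cost is a short wording correction in two appendices and the form, plus one table if data exist. The small downside is that ratings made before and after the correction are not fully comparable.

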14.3 APPENDIX C: Product Insert for Estrace[®]

ESTRACE® Cream

(estradiol vaginal cream, USP, 0.01%)

**WARNING: ENDOMETRIAL CANCER, CARDIOVASCULAR DISORDERS,
BREAST CANCER and PROBABLE DEMENTIA**

Estrogen-Alone Therapy

Endometrial Cancer

There is an increased risk of endometrial cancer in a woman with a uterus who uses unopposed estrogens. Adding a progestin to estrogen therapy has been shown to reduce the risk of endometrial hyperplasia, which may be a precursor to endometrial cancer. Adequate diagnostic measures, including directed or random endometrial sampling when indicated, should be undertaken to rule out malignancy in postmenopausal women with undiagnosed persistent or recurring abnormal genital bleeding [see **WARNINGS, Malignant Neoplasms, Endometrial Cancer**].

Cardiovascular Disorders and Probable Dementia

Estrogen-alone therapy should not be used for the prevention of cardiovascular disease or dementia [see **CLINICAL STUDIES** and **WARNINGS, Cardiovascular Disorders, and Probable Dementia**].

The Women's Health Initiative (WHI) estrogen-alone substudy reported increased risks of stroke and deep vein thrombosis (DVT) in postmenopausal women (50 to 79 years of age) during 7.1 years of treatment with daily oral conjugated estrogens (CE) [0.625 mg]-alone, relative to placebo [see **CLINICAL STUDIES** and **WARNINGS, Cardiovascular Disorders**].

The WHI Memory Study (WHIMS) estrogen-alone ancillary study of WHI reported an increased risk of developing probable dementia in postmenopausal women 65 years of age or older during 5.2 years of treatment with daily CE (0.625 mg) -alone, relative to placebo. It is unknown whether this finding applies to younger postmenopausal women [see **CLINICAL STUDIES** and **WARNINGS, Probable Dementia** and **PRECAUTIONS, Geriatric Use**].

In the absence of comparable data, these risks should be assumed to be similar for other doses of CE and other dosage forms of estrogens.

Estrogens with or without progestins should be prescribed at the lowest effective doses and for the shortest duration consistent with treatment goals and risks for the individual woman.

Estrogen Plus Progestin Therapy

Cardiovascular Disorders and Probable Dementia

Estrogen plus progestin therapy should not be used for the prevention of cardiovascular disease or dementia [see **CLINICAL STUDIES** and **WARNINGS, Cardiovascular Disorders, and Probable Dementia**].

The WHI estrogen plus progestin substudy reported increased risks of DVT, pulmonary embolism (PE), stroke and myocardial infarction (MI) in postmenopausal women (50 to 79 years of age) during 5.6 years of treatment with daily oral CE (0.625 mg) combined with medroxyprogesterone acetate (MPA) [2.5 mg], relative to placebo [see **CLINICAL STUDIES** and **WARNINGS, Cardiovascular Disorders**].

The WHIMS estrogen plus progestin ancillary study of the WHI reported an increased risk of developing probable dementia in postmenopausal women 65 years of age or older during 4 years of treatment with daily CE (0.625 mg) combined with MPA (2.5 mg), relative to placebo. It is unknown whether this finding applies to younger postmenopausal women [see **CLINICAL STUDIES** and **WARNINGS, Probable Dementia and PRECAUTIONS, Geriatric Use**].

Breast Cancer

[figure not shown]
The WHI estrogen plus progestin substudy also demonstrated an increased risk of invasive breast cancer [see **CLINICAL STUDIES** and **WARNINGS, Malignant Neoplasms, Breast Cancer**].

In the absence of comparable data, these risks should be assumed to be similar for other doses of CE and MPA, and other combinations and dosage forms of estrogens and progestins.

Estrogens with or without progestins should be prescribed at the lowest effective doses and for the shortest duration consistent with treatment goals and risks for the individual woman.

DESCRIPTION

Each gram of ESTRACE (estradiol vaginal cream, USP, 0.01%) contains 0.1 mg estradiol in a nonliquefying base containing purified water, propylene glycol, stearyl alcohol, white ceresin wax, mono- and di-glycerides, hypromellose 2208 (4000 cps), sodium lauryl sulfate, methylparaben, edetate di-sodium and *tertiary*-butylhydroquinone. Estradiol is chemically described as estra-1,3,5(10)-triene-3, 17(beta)-diol. It has an empirical formula of C₁₈H₂₄O₂ and molecular weight of 272.37. The structural formula is:

CLINICAL PHARMACOLOGY

Endogenous estrogens are largely responsible for the development and maintenance of the female reproductive system and secondary sexual characteristics. Although circulating estrogens

exist in a dynamic equilibrium of metabolic interconversions, estradiol is the principal intracellular human estrogen and is substantially more potent than its metabolites, estrone and estriol at the receptor level.

The primary source of estrogen in normally cycling adult women is the ovarian follicle, which secretes 70 to 500 mcg of estradiol daily, depending on the phase of the menstrual cycle. After menopause, most endogenous estrogen is produced by conversion of androstenedione, secreted by the adrenal cortex, to estrone by peripheral tissues. Thus, estrone and the sulfate conjugated form, estrone sulfate, are the most abundant circulating estrogens in postmenopausal women.

Estrogens act through binding to nuclear receptors in estrogen-responsive tissues. To date, two estrogen receptors have been identified. These vary in proportion from tissue to tissue.

Circulating estrogens modulate the pituitary secretion of the gonadotropins, luteinizing hormone (LH) and follicle stimulating hormone (FSH), through a negative feedback mechanism.

Estrogens act to reduce the elevated levels of these hormones seen in postmenopausal women.

Pharmacokinetics

Absorption

Estrogen drug products are absorbed through the skin, mucous membranes, and the gastrointestinal tract after release from the drug formulation.

Distribution

The distribution of exogenous estrogens is similar to that of endogenous estrogens. Estrogens are widely distributed in the body and are generally found in higher concentrations in the sex hormone target organs. Estrogens circulate in the blood largely bound to sex hormone binding globulin (SHBG) and albumin.

Metabolism

Exogenous estrogens are metabolized in the same manner as endogenous estrogens. Circulating estrogens exist in a dynamic equilibrium of metabolic interconversions. These transformations take place mainly in the liver. Estradiol is converted reversibly to estrone, and both can be converted to estriol, which is the major urinary metabolite. Estrogens also undergo enterohepatic recirculation via sulfate and glucuronide conjugation in the liver, biliary secretion of conjugates into the intestine, and hydrolysis in the gut followed by reabsorption. In postmenopausal women, a significant proportion of the circulating estrogens exist as sulfate conjugates, especially estrone sulfate, which serves as a circulating reservoir for the formation of more active estrogens.

Excretion

Estradiol, estrone, and estriol are excreted in the urine along with glucuronide and sulfate conjugates.

Special Populations

No pharmacokinetic studies were conducted in special populations, including patients with renal or hepatic impairment.

Drug Interactions

In vitro and in vivo studies have shown that estrogens are metabolized partially by cytochrome P450 3A4 (CYP3A4). Therefore, inducers or inhibitors of CYP3A4 may affect estrogen drug metabolism. Inducers of CYP3A4 such as St. John's Wort preparations (*Hypericum perforatum*), phenobarbital, carbamazepine, and rifampin may reduce plasma concentrations of estrogens, possibly resulting in a decrease in therapeutic effects and/or changes in the uterine bleeding profile. Inhibitors of CYP3A4 such as erythromycin, clarithromycin, ketoconazole, itraconazole, ritonavir and grapefruit juice may increase plasma concentrations of estrogens and may result in side effects.

CLINICAL STUDIES

Women's Health Initiative Studies

The WHI enrolled approximately 27,000 predominantly healthy postmenopausal women in two substudies to assess the risks and benefits of daily oral CE (0.625 mg)-alone or in combination with MPA (2.5 mg) compared to placebo in the prevention of certain chronic diseases. The primary endpoint was the incidence of coronary heart disease (CHD) (defined as nonfatal MI, silent MI and CHD death), with invasive breast cancer as the primary adverse outcome. A "global index" included the earliest occurrence of CHD, invasive breast cancer, stroke, PE, endometrial cancer (only in the CE plus MPA substudy), colorectal cancer, hip fracture, or death due to other cause. These substudies did not evaluate the effects of CE or CE plus MPA on menopausal symptoms.

WHI Estrogen-Alone Substudy

The WHI estrogen-alone substudy was stopped early because an increased risk of stroke was observed, and it was deemed that no further information would be obtained regarding the risks and benefits of estrogen-alone in predetermined primary endpoints.

Results of the estrogen-alone substudy, which included 10,739 women (average 63 years of age, range 50 to 79; 75.3 percent White, 15.1 percent Black, 6.1 percent Hispanic, 3.6 percent Other), after an average follow-up of 7.1 years are presented in Table 1.

TABLE 1 -Relative and Absolute Risk Seen in the Estrogen-Alone Substudy of WHI^a

Event	Relative Risk CE vs. Placebo (95% nCI ^b)	CE	Placebo
		Absolute Risk per 10,000 Women-Years	
CHD events ^c	0.95 (0.78-1.16)	54	57
Non-fatal MI ^c	0.91 (0.73-1.14)	40	43
CHD death ^c	1.01 (0.71-1.43)	16	16
All Stroke ^c	1.33 (1.15-1.68)	45	33
Ischemic stroke ^c	1.55 (1.19-2.01)	38	25
Deep vein thrombosis ^{c,d}	1.47 (1.06-2.06)	23	15
Pulmonary embolism ^c	1.37 (0.90-2.07)	14	10
Invasive breast cancer ^c	0.80 (0.62-1.04)	28	34
Colorectal cancer ^c	1.08 (0.75-1.55)	17	16
Hip fracture ^c	0.65 (0.45-0.94)	12	19
Vertebral fractures ^{c,d}	0.64 (0.44-0.93)	11	18
Lower arm/wrist fractures ^{c,d}	0.58 (0.47-0.72)	35	59
Total fractures ^{c,d}	0.71 (0.64-0.80)	144	197
Death due to other causes ^{e,f}	1.08 (0.88-1.32)	53	50
Overall mortality ^{c,d}	1.04 (0.88-1.22)	79	75
Global index ^g	1.02 (0.92-1.13)	206	201

^a Adapted from numerous WHI publications. WHI publications can be viewed at www.nhlbi.nih.gov/whi.

^b Nominal confidence intervals unadjusted for multiple looks and multiple comparisons.

^c Results are based on centrally adjudicated data for an average follow-up of 7.1 years.

^d Not included in "global index".

^e Results are based on an average follow-up of 6.8 years.

^f All deaths, except from breast or colorectal cancer, definite or probable CHD, PE or cerebrovascular disease.

^g A subset of the events was combined in a "global index" defined as the earliest occurrence of CHD events, invasive breast cancer, stroke, pulmonary embolism, endometrial cancer, colorectal cancer, hip fracture, or death due to other causes.

For those outcomes included in the WHI "global index" that reached statistical significance, the absolute excess risk per 10,000 women-years in the group treated with CE-alone was 12 more strokes, while the absolute risk reduction per 10,000 women-years was 7 fewer hip fractures¹. The absolute excess risk of events included in the "global index" was a non-significant 5 events per 10,000 women-years. There was no difference between the groups in terms of all-cause mortality.

No overall difference for primary CHD events (nonfatal MI, silent MI and CHD death) and invasive breast cancer incidence in women receiving CE-alone compared with placebo was reported in final centrally adjudicated results from the estrogen-alone substudy, after an average follow-up of 7.1 years.

Centrally adjudicated results for stroke events from the estrogen-alone substudy, after an average follow-up of 7.1 years, reported no significant differences in distribution of stroke subtypes or severity, including fatal strokes, in women receiving CE-alone compared to

placebo. Estrogen-alone increased the risk for ischemic stroke, and this excess risk was present in all subgroups of women examined².

Timing of the initiation of estrogen-alone therapy relative to the start of menopause may affect the overall risk benefit profile. The WHI estrogen-alone substudy stratified by age showed in women 50 to 59 years of age a non-significant trend toward reduced risk for CHD [*hazard ratio (HR) 0.63 (95 percent CI, 0.36-1.09)*] and overall mortality [*HR 0.71 (95 percent CI, 0.46-1.11)*].

WHI Estrogen Plus Progestin Substudy

The WHI estrogen plus progestin substudy was also stopped early. According to the predefined stopping rule, after an average follow-up of 5.6 years of treatment, the increased risk of breast cancer and cardiovascular events exceeded the specified benefits included in the “global index.” The absolute excess risk of events included in the “global index” was 19 per 10,000 women-years.

For those outcomes included in the WHI “global index” that reached statistical significance after 5.6 years of follow-up, the absolute excess risks per 10,000 women-years in the group treated with CE plus MPA were 7 more CHD events, 8 more strokes, 10 more PEs, and 8 more invasive breast cancers, while the absolute risk reductions per 10,000 women-years were 6 fewer colorectal cancers and 5 fewer hip fractures.

Results of the CE plus MPA substudy, which included 16,608 women (average 63 years of age, range 50 to 79; 83.9 percent White, 6.8 percent Black, 5.4 percent Hispanic, 3.9 percent Other), are presented in Table 2. These results reflect centrally adjudicated data after an average follow-up of 5.6 years.

TABLE 2 -Relative and Absolute Risk Seen in the Estrogen Plus Progestin Substudy of WHI at an Average of 5.6 Years

Event	Relative Risk CE/MPA vs. Placebo (95% nCI ^c)	CE/MPA	Placebo
		n = 8,506	n = 8,102
		Absolute Risk per 10,000 Women-Years	
CHD events	1.23 (0.99–1.53)	41	34
Non-fatal MI	1.28 (1.00–1.63)	31	25
CHD death	1.10 (0.70–1.75)	8	8
All Strokes	1.31 (1.03–1.68)	33	25
Ischemic stroke	1.44 (1.09–1.90)	26	18
Deep vein thrombosis ^d	1.95 (1.43–2.67)	26	13
Pulmonary embolism	2.13 (1.45–3.11)	18	8
Invasive breast cancer ^e	1.24 (1.01–1.54)	41	33
Colorectal cancer	0.61 (0.42–0.87)	10	16
Endometrial cancer ^d	0.81 (0.48–1.36)	6	7
Cervical cancer ^d	1.44 (0.47–4.42)	2	1
Hip fracture	0.67 (0.47–0.96)	11	16
Vertebral fractures ^d	0.65 (0.46–0.92)	11	17
Lower arm/wrist fractures ^d	0.71 (0.59–0.85)	44	62
Total fractures ^d	0.76 (0.69–0.83)	152	199
Overall Mortality ^f	1.00 (0.83–1.19)	52	52
Global Index ^g	1.13 (1.02–1.25)	184	165

^a Adapted from numerous WHI publications. WHI publications can be viewed at www.nhlbi.nih.gov/whi.

^b Results are based on centrally adjudicated data.

^c Nominal confidence intervals unadjusted for multiple looks and multiple comparisons.

^d Not included in “global index.”

^e Includes metastatic and non-metastatic breast cancer, with the exception of *in situ* cancer.

^f All deaths, except from breast or colorectal cancer, definite or probable CHD, PE or cerebrovascular disease.

^g A subset of the events was combined in a “global index” defined as the earliest occurrence of CHD events, invasive breast cancer, stroke, pulmonary embolism, colorectal cancer, hip fracture, or death due to other causes.

Timing of the initiation of estrogen plus progestin therapy relative to the start of menopause may affect the overall risk benefit profile. The WHI estrogen plus progestin substudy stratified by age showed in women 50 to 59 years of age, a non-significant trend toward reduced risk for overall mortality [HR 0.69 (95 percent CI, 0.44-1.07)].

Women’s Health Initiative Memory Study

The WHIMS estrogen-alone ancillary study of WHI enrolled 2,947 predominantly healthy hysterectomized postmenopausal women 65 to 79 years of age and older (45 percent were 65 to 69 years of age; 36 percent were 70 to 74 years of age; 19 percent were 75 years of age and older) to evaluate the effects of daily CE (0.625 mg)-alone on the incidence of probable dementia (primary outcome) compared to placebo.

After an average follow-up of 5.2 years, the relative risk of probable dementia for CE-alone versus placebo was 1.49 (95 percent CI, 0.83-2.66). The absolute risk of probable dementia for CE-alone versus placebo was 37 versus 25 cases per 10,000 women-years. Probable dementia as defined in this study included Alzheimer’s disease (AD), vascular dementia (VaD) and mixed types (having features of both AD and VaD). The most common classification of probable dementia in the treatment group and the placebo group was AD. Since the ancillary study was

conducted in women 65 to 79 years of age, it is unknown whether these findings apply to younger postmenopausal women [see **BOXED WARNINGS, WARNINGS, Probable Dementia and PRECAUTIONS, Geriatric Use**].

The WHIMS estrogen plus progestin ancillary study of WHI enrolled 4,532 predominantly healthy postmenopausal women 65 years of age and older (47 percent were 65 to 69 years of age; 35 percent were 70 to 74 years; 18 percent were 75 years of age and older) to evaluate the effects of daily CE (0.625 mg) plus MPA (2.5 mg) on the incidence of probable dementia (primary outcome) compared to placebo.

After an average follow-up of 4 years, the relative risk of probable dementia for CE plus MPA versus placebo was 2.05 (95 percent CI, 1.21-3.48). The absolute risk of probable dementia for CE plus MPA versus placebo was 45 versus 22 per 10,000 women-years. Probable dementia as defined in this study included AD, VaD and mixed types (having features of both AD and VaD). The most common classification of probable dementia in the treatment group and the placebo group was AD. Since the ancillary study was conducted in women 65 to 79 years of age, it is unknown whether these findings apply to younger postmenopausal women [see **WARNINGS, Probable Dementia and PRECAUTIONS, Geriatric Use**].

When data from the two populations were pooled as planned in the WHIMS protocol, the reported overall relative risk for probable dementia was 1.76 (95 percent CI, 1.19-2.60). Differences between groups became apparent in the first year of treatment. It is unknown whether these findings apply to younger postmenopausal women [see **WARNINGS, Probable Dementia and PRECAUTIONS, Geriatric Use**].

INDICATIONS AND USAGE

ESTRACE (estradiol vaginal cream, USP, 0.01%) is indicated in the treatment of moderate to severe symptoms of vulvar and vaginal atrophy due to menopause.

CONTRAINdications

ESTRACE (estradiol vaginal cream, USP, 0.01%) should not be used in women with any of the following conditions:

1. Undiagnosed abnormal genital bleeding.
2. Known, suspected, or history of cancer of the breast.
3. Known or suspected estrogen-dependent neoplasia.
4. Active DVT, PE or history of these conditions.
5. Active arterial thromboembolic disease (for example, stroke, MI) or a history of these conditions.
6. Known anaphylactic reaction or angioedema to ESTRACE (estradiol vaginal cream, USP, 0.01%).
7. Known liver dysfunction or disease.
8. Known protein C, protein S, or antithrombin deficiency, or other known thrombophilic disorders.
9. Known or suspected pregnancy.

WARNINGS

See **BOXED WARNINGS**.

Systemic absorption may occur with the use of ESTRACE (estradiol vaginal cream, USP, 0.01%). The warnings, precautions, and adverse reactions associated with oral estrogen treatment should be taken into account.

1. Cardiovascular Disorders

An increased risk of stroke and DVT has been reported with estrogen-alone therapy. An increased risk of PE, DVT, stroke and MI has been reported with estrogen plus progestin therapy. Should any of these occur or be suspected, estrogen with or without progestin therapy should be discontinued immediately.

Risk factors for arterial vascular disease (e.g., hypertension, diabetes mellitus, tobacco use, hypercholesterolemia, and obesity) and/or venous thromboembolism (VTE) (e.g., personal history or family history of VTE, obesity, and systemic lupus erythematosus) should be managed appropriately.

a. Stroke

In the WHI estrogen-alone substudy, a statistically significant increased risk of stroke was reported in women 50 to 79 years of age receiving daily CE (0.625 mg)-alone compared to women in the same age group receiving placebo (45 versus 33 per 10,000 women-years). The increase in risk was demonstrated in year one and persisted [see **CLINICAL STUDIES**]. Should a stroke occur or be suspected, estrogen-alone therapy should be discontinued immediately.

Subgroup analyses of women 50 to 59 years of age suggest no increased risk of stroke for those women receiving CE (0.625 mg)-alone versus those receiving placebo (18 versus 21 per 10,000 women-years)³.

In the WHI estrogen plus progestin substudy, a statistically significant increased risk of stroke was reported in women 50 to 79 years of age receiving daily CE (0.625 mg) plus MPA (2.5 mg) compared to women in the same age group receiving placebo (33 versus 25 per 10,000 women-years) [see **CLINICAL STUDIES**]. The increase in risk was demonstrated after the first year and persisted³. Should a stroke occur or be suspected, estrogen plus progestin therapy should be discontinued immediately.

b. Coronary Heart Disease

In the WHI estrogen-alone substudy, no overall effect on coronary heart disease (CHD) events (defined as nonfatal MI, silent MI and CHD death) was reported in women receiving estrogen-alone compared to placebo⁴ [see **CLINICAL STUDIES**].

